1.3.11 Data Analysis

Analysis will be performed using Qualtrics statistical software. Analyses will be performed on all control and experimental group data. The control group is defined as the standard care without presence of support person, whereas the intervention group is all those receiving standard care with the presence of a support person in the procedure room. Demographic, behavioral, and clinical characteristics will be compared between the two arms using frequency tests, Student's ttest, chi-squared tests, and two-way ANOVA, where appropriate. The change in pain score, as assessed by VAS, from baseline to recovery room will be compared within each group using paired Student's t-test if the data are normally distributed or Wilcoxon signed-rank test if the data do not follow a Gaussian distribution. Similarly, the difference in the change in VAS scores between the

study arms will be compared using Student's t- or Mann-Whitney U tests, where appropriate. Questionnaire answers will be compared between both arms of the study using chi-squared statistical analysis. Statistical analysis will be performed by both the Principal Investigator and statistician.

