1.3 Design and methodology

1.3.1 Research design and General Methodological Approach

This study will be designed as a randomized, controlled trial to compare pain and anxiety levels before, during, and after in-clinic abortion in patients with and without a support person in the abortion procedure room. Each procedure day will be randomized into "support person day" ("intervention group") or "non-support person day" ("control group"). This randomization process was chosen as the most effective way to randomize without compromising patient care and study validity. Limitations to the physical space of the health center prevent patient randomization because there is no way to avoid patients knowing which arm of the study they are in: the intervention arm or the control arm.

Randomization will occur at the beginning of each procedure day by a research assistant who will pull from an opaque envelope that contains ten slips of paper, five will be marked with 'A' and the other five marked with 'B'. The half marked 'A' will indicate the procedure day will be assigned as an "intervention" day, and the other half marked 'B' will indicate the day will be assigned as a "control" day. After all ten slips of paper are pulled and ten of the procedure days have been randomized, the research assistant will replace the ten slips of paper and begin the same randomization process until the designated number of participants have been enrolled. The research assistant will initiate enrollment of patients in the study after they have consented for the abortion procedure.

All patients who present at PPSWCF's Tampa Health Center for a dilation and curettage (D&C), whether for elective pregnancy termination or management of early pregnancy complications and who are proficient enough in English to consent and understand the study procedures are eligible for participation and enrollment. Support people will be eligible for participation and enrollment if they are 18 years of age or older, are privately selected by the patient to be their support person, and who are proficient enough in English to consent and understand the study procedures. Support people for minors will be privately selected by the patient in conjunction with their parent/guardian consent.

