1.3.2 Sample Size

A total of 400 subjects will be enrolled in this study; 200 participants will enroll in the control arm and 200 will enroll in the intervention arm. Within these two arms, 100 subjects will be "patients" and "support persons." "Patients" are defined as people who will receive an in-clinic abortion on the day of their participation. "Support persons" are the individuals whom the patient chooses to accompany them during the in-clinic abortion procedure. Support persons will only actually accompany patients in the in-clinic procedure room if they are randomized to the

intervention arm of this study. Health care providers will also be invited to participate in this research study—and enrollment numbers will depend upon the amount of unduplicated staff who will perform or assist with the D&C procedure on days when enrollment will occur. "Health care providers" include the physician performing the abortion and nurses assisting the physician within the abortion procedure room.

Prior studies indicate a 20mm difference in VAS is clinically significant and that the common standard deviation for VAS scores is 23 mm [8]. Based on these assumptions, a sample size of 28 with 14 women in each arm will have 90% power to detect at least a 20mm difference between the change in pain score from baseline, to during the procedure, to after the procedure between the two groups, using a Student's t-test evaluated at the 2-sided 0.05 significance level.

We have chosen a larger sample size to also provide a representative sample of our patient population for our secondary aims of patient and support person satisfaction as well as nurse and physician satisfaction. This sample size was calculated based on the total number of in-clinic abortion patients seen in the Tampa Health Center in 2015 with a Confidence Level of 95% and a Confidence interval of 10.

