1.3.5. Criteria for discontinuation

Participation will be discontinued following an eligibility screening for any of the following reasons:

- Unable to receive an abortion at the health center as determined by the physician
- Subject no longer wishes to have an in-clinic abortion procedure
- The support person is perceived by staff as being dangerous or threatening to the safety of staff or patients
- Subject is found to meet exclusion criteria after informed consent has been signed
- The study is discontinued
- Subjects chooses to end participation

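### Section 1.3.11 defines the analysis groups by whether a support person was present, while section 1.3.1 forms the arms by randomised procedure day; the two need reconciling

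*Protocol*

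**What the plan says.** Four places in the protocol bear on this.

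- **Section 1.3.1** sets the allocation: "Each procedure day will be randomized into" a support person day or a non-support person day. It labels these the intervention group and the control group. A slip drawn at the start of the day decides, before that day's patients are enrolled.
- **Section 1.3.2** ties presence to allocation: "Support persons will only actually accompany patients in the in-clinic procedure room if they are randomized to the" intervention arm.
- **Section 1.3.11** describes the groups for analysis: "The control group is defined as the standard care without presence of support person", and "the intervention group is all those receiving standard care with the presence of a support person in the procedure room". It also says that "Analyses will be performed on all control and experimental group data". The assigned day does not appear in either description.
- **Section 1.3.5** lists reasons for ending participation, among them "The support person is perceived by staff as being dangerous or threatening to the safety of staff or patients" and "Subjects chooses to end participation". It does not mention moving anyone to the other arm.

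**The concern.** Section 1.3.11 words its two descriptions as rules for who belongs to which group, and the criterion is what happened in the room. Section 1.3.1 uses a different criterion, the slip drawn that morning. A group definition matters only when the two differ, and the protocol foresees conditions in which they could. Section 1.6 names provider support as a leading worry and expects frustration among patients who want company and may not have it.

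Section 1.3.12 relies on randomisation to make the groups alike. That holds for groups formed by day. It need not hold for groups formed by presence, because a patient who ends up alone on an intervention day, or accompanied on a control day, may differ from the rest in pain or anxiety. Both primary aims, VAS pain and STAI anxiety, would be affected.

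Discontinuation under section 1.3.5 is a second and separate route. The day is already randomised when the patient consents, so leaving out a patient discontinued after consent is an exclusion after randomisation.

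**Working it through.** **Side by side**

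| Situation | Arm under 1.3.1 | Group under 1.3.11, read literally |
|---|---|---|
| Intervention day, support person present | Intervention | Intervention |
| Control day, no support person | Control | Control |
| Intervention day, support person did not enter or left | Intervention | Control |
| Control day, support person present (a protocol deviation) | Control | Intervention |
| Participation ended under 1.3.5 | Arm of the day | Not addressed; no reassignment stated |

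The first two rows are full compliance, where the definitions coincide. The third and fourth are where they conflict.

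**Inputs for an illustration**

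- n = 100 patients per arm, reading section 1.3.2 as 100 patients and 100 support persons in each arm.
- Target difference 20 mm and SD 23 mm, from section 1.3.2.
- f, the share of intervention-day patients unaccompanied: not in the documents; assumed 2% to 10%.
- g, how much worse their pain outcome is than that of the remaining patients: not in the documents; assumed 10 to 20 mm.
- No true effect, so control days contain the same share f of such patients.

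The point rests on no figure that the plan states. The nearby calculation of 14 women per arm for 90% power does not reproduce: 2 × (1.96 + 1.28)² × 23² / 20² gives 28 per arm, and 14 per arm gives about 60% power with the t-test. That is a separate matter and does not enter below.

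**Regrouping by presence**

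Set the mean of the remaining patients to 0. The accompanied group then has mean 0. The unaccompanied group holds 100 control-day patients plus 100f moved patients, with mean (100fg + 100fg) / (100 + 100f). The bias is therefore 2fg / (1 + f).

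The last column uses SE = 23 × √(1/(100 − 100f) + 1/(100 + 100f)), a normal approximation, and no allowance for clustering by day.

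| f | g (mm) | Bias (mm) | Two-sided type I error |
|---|---|---|---|
| 2% | 10 | 0.4 / 1.02 = 0.39 | 5.2% |
| 2% | 20 | 0.8 / 1.02 = 0.78 | 5.7% |
| 5% | 10 | 1.0 / 1.05 = 0.95 | 6.0% |
| 5% | 20 | 2.0 / 1.05 = 1.90 | 9.0% |
| 10% | 10 | 2.0 / 1.10 = 1.82 | 8.6% |
| 10% | 20 | 4.0 / 1.10 = 3.64 | 19.9% |

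If the 20 mm is measured from the arm mean instead of from the remaining patients, 5% gives 20 × 5/95 + 20 × 5/105 = 2.0 mm, and 10% gives 20 × 10/90 + 20 × 10/110 = 4.0 mm. Hence the range of about 0.4 to 4 mm.

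**Direction**

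The signs above favour the support person. If instead a share f of control-day patients, g mm worse, were accompanied and counted as intervention, the same formula applies with the sign reversed.

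**Dropping instead of regrouping**

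If such patients are dropped on intervention days only, the intervention mean is 0 and the control mean is fg. At g = 20 mm this is 0.05 × 20 = 1.0 mm and 0.10 × 20 = 2.0 mm. Measured from the arm mean it is 20 × 5/95 = 1.05 mm and 20 × 10/90 = 2.22 mm.

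**Cost of analysing by assigned day**

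The bias is zero. If unaccompanied patients gain nothing, a true 20 mm effect is diluted to 20 × (1 − f): 19.6, 19 and 18 mm at 2%, 5% and 10%. With 100 per arm and SD 23 mm, power stays above 99%, again ignoring clustering by day.

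**The case against.** The strongest reply is that the sentence in 1.3.11 only describes what each arm receives. Section 1.3.1 has already fixed the labels, section 1.3.4 uses the same shorthand for the intervention group, and 1.3.11 goes on to compare study arms. This reading is possible, so a reader who infers a declared as-treated analysis goes too far: the text is ambiguous. It remains true that the only membership wording in the analysis section is based on presence and omits the assigned day.

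Other replies also have force:

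- **Removed cases.** A reader might infer that patients whose support person is removed would change arm. Section 1.3.5 ends their participation and names no reassignment, so the documents point to exclusion.
- **Where removal arises.** One might assume that it falls mainly on intervention days. Support persons are enrolled and on site in both arms, and the criterion is not limited to the procedure room, so the documents do not show this. If losses were alike in both arms, the bias from dropping would shrink.
- **Accompanied control-day patients.** Section 1.3.2 rules this out, and section 2 allows provider discretion only for patients who decline the study. It can arise only as a deviation.
- **Size.** The rates and excess pain are assumed. The standard error of the difference is about 23 × √(2/100) = 3.3 mm before clustering, so the smaller biases lie well within noise. The planned outcome is change from expected pain; if patients who deviate also expect more pain, the excess in the change score is smaller.
- **Analysis sets.** A full definition may stand in an SAP that is not shown, so its absence is no finding. The point is confined to wording that the protocol does contain.

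**Conclusion.** The point holds as a conflict of wording. Section 1.3.11 groups by presence and section 1.3.1 by randomised day; they agree under full compliance and disagree for patients who deviate. Discontinuation under 1.3.5 is a separate exclusion after randomisation.

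A reader might conclude that the randomised comparison is lost, or that the result must be biased in favour of the support person. The documents support neither. The groups would differ from the randomised ones only by the patients who deviate, no rate is given, and the direction depends on who they are.

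Under the stated assumptions the bias is about 0.4 to 4 mm from regrouping (2% to 20% of the 20 mm target) and about 1 to 2 mm from dropping 5% to 10% of intervention-day patients who are 20 mm worse. At 2% deviation it is under 1 mm. The change is worth making because it removes the ambiguity at essentially no cost in power.

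**What to change.** Replace the two group descriptions in section 1.3.11 with: *Patients are analysed in the arm assigned to their procedure day, whether or not a support person was in the room.*

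Keep VAS and STAI outcomes already collected, or still obtainable, from discontinued patients who agree. This leaves the discontinuation criteria themselves untouched.

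Record for each patient whether the support person was present, and report actual presence descriptively or as a sensitivity analysis. Section 1.3.8.1 already calls for deviations to be recorded, so this needs one explicit item on a form.

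The cost is one sentence in the analysis section, a line on retaining data and one tick-box. The sample size does not change.

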1.3.8.1 Patient Procedure and Questionnaires

- 1) After patients have consented for the D&C procedure and the study, they will complete a paper questionnaire. This questionnaire will contain demographic information and type of sedation chosen. Additionally, subjects will record their baseline level of expected pain prior to the start of the procedure. The subject will also complete the State Trait Anxiety Inventory (STAI) after the informed consent process and before the procedure starts.
- 2) On randomized intervention days, the patient will be accompanied in the procedure room by a support person.
- 3) The study physician will enter the room and perform the abortion procedure in the usual manner. The abortion procedure will remain the same on intervention days as on control days. Immediately after the procedure, the patient will complete the second 100mm VAS. Any deviations from this protocol will be recorded.
- 4) Once the patient is in the post-abortion recovery room, the patient will complete the STAI again, a post-procedure questionnaire, and the final pain level on the 100mm VAS will be recorded at least ten minutes after arrival to the recovery room. After all questionnaires have been completed and returned to research staff, the subject will be given their reimbursement gift card for participation.
- 5) The patient's complete questionnaires will be manually entered in the Qualtrics data management software which will only be managed by designated research staff. Study documents, including surveys, will be stored in a locked filing cabinet and will be accessed by research personnel only.

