4. RESEARCH INSTRUMENTS/QUESTIONNAIRES

4.1 SUBJECT DEMOGRAPHIC QUESTIONNAIRE – INTERVENTION ARM

Please fill in the information below, if applicable: Age: _____ Gestational age (How many weeks pregnant are you?) Number of children: _____ Number of previous abortions: Religion: Please circle your answers below: Ethnicity: Hispanic Non-Hispanic Race: American Indian or Alaska Native Asian Black or African American Native Hawaiian or other Pacific Islander White Two or more races **Marital Status**: Single Married Divorced Widowed Separated Are you using your insurance for the procedure? No Yes Are you receiving sedation for the procedure? Yes No What is your relation to the patient/support person?

${\bf 4.1~SUBJECT~DEMOGRAPHIC~QUESTIONNAIRE-CONTROL~ARM}$

Please fill in the information below, if applicable:

Age:						
Gestational	age (H	ow many we	eks pregnant are	e you?)		
Number of	childre	n:				
Number of j	previou	ıs abortions:				
Religion:						
	your a	nswers below				
	Non-	Hispanic				
Race:	Ame	rican Indian o	or Alaska Native			
	Asia	n				
	Black	k or African A	American			
	Nativ	ve Hawaiian o	or other Pacific Isl	lander		
	Whit	e				
	Two	or more race	S			
Marital Sta	tus:	Single	Married	Divorced	Widowed	Separated
Are you usi	ng youi	r insurance f	or the procedure	?	Yes	No
Are you rec	eiving s	sedation for	the procedure?	Yes	No	
What is you	ır relati	ion to the pa	tient/support per	rson?		

4.2 POST-PROCEDURE QUESTIONNAIRE FOR PATIENT - INTERVENTION ARM Please circle your answers below:

1.	I would rate my overall satisfaction with the procedure as: Very satisfied
	Somewhat satisfied
	Neutral
	Somewhat dissatisfied
	Very dissatisfied
2.	The amount of discomfort I experienced during the procedure was acceptable. Definitely yes
	Probably yes
	Neutral
	Probably not
	Definitely not
3.	I feel that the amount of support I received from my support person in the procedure room helped decrease my pain. Definitely yes
	Probably yes
	Neutral
	Probably not
	Definitely not
4.	I feel that I received all the support I needed from my support person in the procedure room. Definitely yes
	Probably yes
	Neutral
	Probably not
	Definitely not
La	st updated: 4/10/2017

5. The presence of my support person in the procedure room made me feel uncomfortable.
Definitely yes
Probably yes
Neutral
Probably not
Definitely not
6. If you were uncomfortable in the procedure room, were you uncomfortable due to any of the following: (Circle all applicable options)

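### The between-arm pain test uses neither the patient characteristics already collected nor the randomised procedure day, and significance tests of those characteristics correct nothing

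*Protocol*

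**What the plan says.** Section 1.3.1 sets the unit of randomisation: "Each procedure day will be randomized into" a support-person day or a control day. A research assistant draws a slip at the start of the day from a block of ten, five per arm, and enrolment follows. The section adds that patients cannot be kept from knowing their arm.

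Before the procedure, the questionnaire form (section 4.1) asks for age, number of children, number of previous abortions, sedation and "Gestational age (How many weeks pregnant are you". Section 1.3.8.1 says "This questionnaire will contain demographic information and type of sedation chosen", and that "subjects will record their baseline level of expected pain prior to the start of the procedure".

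Section 1.3.11 uses these data as follows.

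- **Characteristics:** "Demographic, behavioral, and clinical characteristics will be compared between the two arms using frequency tests", with Student's t, chi-squared and two-way ANOVA as further options.
- **Pain within arms:** change "from baseline to recovery room will be compared within each group using paired Student's t-test", or a signed-rank test.
- **Pain between arms:** the difference in VAS change between the "study arms will be compared using Student's t- or Mann-Whitney U tests, where appropriate".
- **STAI:** no method is named specifically.

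No adjusted model, covariate or term for the day appears. Section 1.3.12 relies on randomisation to make the groups similar.

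**The concern.** A test of characteristics between arms does not alter the estimated pain difference. If it is non-significant, readers may take it as reassurance; if it is significant, the plan provides no adjusted analysis. Meanwhile the two-sample test treats patients as if each had been randomised individually.

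Two features of the design make this matter more than usual. First, patient mix is balanced only through days, so chance differences can be larger than with individual randomisation. Second, the draw precedes enrolment and the research assistant's role covers both, so who agrees to join may depend on the arm. Section 1.6 expects frustration among patients who want a support person and are refused. Section 2 notes that a patient outside the study might still have one at the provider's discretion.

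At stake are some precision, the measured part of any difference in mix, and an error rate that matches the design.

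**Working it through.** **Inputs from the protocol (section 1.3.2).** SD 23 mm, target difference 20 mm, two-sided 0.05, and 200 participants per arm enrolled as patient and support-person pairs, read as 100 patients per arm.

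**Assumptions, because the protocol gives no values.** R² of the four characteristics 0.05 to 0.20; number of procedure days 10 to 30; intraclass correlation (ICC) within day 0.02 to 0.10. The SD of 23 mm is applied to the change score, as section 1.3.2 does. If 23 mm is the SD of a single score, this needs a correlation of 0.5 between the two scores.

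**The plan's own figure.** n per arm = 2 × [23 × (1.960 + 1.282) / 20]² = 27.8, so 28 per arm. The protocol states 28 in total, 14 per arm, so its figure is not reproduced. That is a separate error and is not evidence for this point; the calculations below use 100 per arm.

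**Step 1: precision from adjustment, patients treated as independent.** SE = 23 × √(1 − R²) × √(2/100).

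| Assumed R² | Residual SD (mm) | SE (mm) | 95% CI half-width (mm) | Power for 10 mm |
|---|---|---|---|---|
| 0 | 23.0 | 3.25 | 6.4 | 86% |
| 0.05 | 22.4 | 3.17 | 6.2 | 88% |
| 0.10 | 21.8 | 3.09 | 6.0 | 90% |
| 0.20 | 20.6 | 2.91 | 5.7 | 93% |

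The SE falls by 3% to 11%. Power for 20 mm exceeds 99.9% in every row. As an equivalent number of patients, 1/(1 − R²) gives 1.05, 1.11 and 1.25.

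**Step 2: chance imbalance when days are randomised.** Design effect DE = 1 + (m − 1) × ICC, with m = 200 / days. For a characteristic with 50% prevalence, the SD of the arm difference is √(0.25 × 2/100 × DE).

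| Days (m) | ICC | DE | SD of imbalance (points) | Chance of more than 10 points |
|---|---|---|---|---|
| any | 0 | 1.00 | 7.1 | 16% |
| 10 (20) | 0.02 | 1.38 | 8.3 | 23% |
| 10 (20) | 0.10 | 2.90 | 12.0 | 41% |
| 30 (6.7) | 0.02 | 1.11 | 7.5 | 18% |
| 30 (6.7) | 0.10 | 1.57 | 8.9 | 26% |

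**Step 3: what an imbalance does to the estimate.** A 0.3 SD difference in a characteristic correlated 0.3 with pain (both assumed) shifts the unadjusted difference by 0.3 × 0.3 × 23 = 2.07 mm. That is about a tenth of 20 mm and 2.07 / 3.25 = 0.64 SE. The SD of a standardised difference is √(2/100 × DE). An imbalance that large therefore has a chance of about 3% with independent patients and 7% to 21% with 10 days over the assumed ICC range.

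**Step 4: ignoring the day in the outcome test.** With the same range for the outcome ICC, the true two-sided error of a nominal 5% test is about 2 × [1 − Φ(1.96/√DE)]. This gives 0.06 to 0.12 with 30 days and 0.10 to 0.25 with 10 days. Patient-level covariates alone would not repair this.

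**The case against.** Much of the opposing case stands. An unadjusted t or Mann-Whitney test is not invalid for lack of covariates. Adjusted models are often left to a statistical analysis plan, which may exist and could add one. Step 1 assumes independent patients, and patient-level covariates need not reduce between-day variance by the same fraction. The 2.1 mm shift is random error unless recruitment differs by arm, and it is small.

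A reader might also infer several stronger points that the protocol does not support:

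- **That the characteristics are known to predict pain.** The protocol does not say so; every R² and correlation here is assumed.
- **That few days are randomised.** No number is given, only repeating blocks of ten and three recruitment months in the timeline (section 5).
- **That pain is analysed with no regard to baseline.** The change score already subtracts expected pain.
- **That an unadjusted anxiety comparison is fixed.** Section 1.3.11 names no method for the STAI.

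Finally, comparing characteristics between arms has a use here: with an unconcealed daily draw it can reveal differential recruitment. That supports keeping the comparison in descriptive form. It does not make a p-value a correction.

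What the objection does not remove is that section 1.3.11 goes beyond silence. It names the between-arm pain test, and that test can take neither a covariate nor the day.

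**Conclusion.** The point holds in a limited form. The named pain test leaves out both the collected characteristics and the randomised day, and the tests of characteristics correct no difference in patient mix, whether it arises by chance between days or through enrolment after a known allocation.

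The gain from covariates is modest: an SE reduction of 3% to 11% for an assumed R² of 0.05 to 0.20. Power for 20 mm at 100 patients per arm is not in question. Adjustment would correct only the measured part of any recruitment difference. Ignoring the day is the larger fault in the same sentence of the plan, but its size depends on an ICC and a number of days that the protocol does not state. The change is worth making because it is cheap and the data are already collected.

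**What to change.** In section 1.3.11:

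1. Keep the change in VAS from baseline as the pain outcome. Estimate the arm difference with a linear mixed model with procedure day as a random effect and a small-sample correction, or an equivalent day-level analysis.
2. Adjust for a short prespecified list whose values the arm cannot alter: age, gestational age, number of children and number of previous abortions.
3. Use the same model for the pre-to-post STAI comparison.
4. Do not adjust for sedation, which is recorded after the day's draw. Let expected pain enter only through the change score, and state that it is also recorded after allocation and may be affected by knowledge of the arm. Section 1.3.12 already concedes this for baseline anxiety.
5. Replace the significance tests of characteristics with a descriptive table by arm, for example with standardised differences, as a check on differential recruitment.

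The cost is slightly more analysis work, a stated rule for missing covariates, and software that can fit the model; whether the Qualtrics package named in section 1.3.11 can do so should be confirmed. The date of each procedure must be in the data set. No new patient questions are needed.

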1.1.2 Hypotheses and Objectives

Hypotheses:

Social support in the abortion procedure room will decrease perceived pain and anxiety levels and increase satisfaction for the patient.

- 1. Social support in the procedure room influenced the patient's health outcomes in the following areas:
 - 1. Decreased pain
 - 2. Decreased anxiety
 - 3. Increased patient satisfaction
- 2. The social support person will report that they were able to give effective support to the patient.
- 3. The physician and the nurse will find the support person effective in supporting the patient.

Null Hypothesis:

- 1. Social support in the abortion procedure room will not change patient levels of perceived pain, anxiety, or satisfaction.
- 2. The social support person will report they did not give adequate support.
- 3. The health care provider and the surgical assistant will not find the support person effective

in supporting the patient.

Objectives

Primary Aims:

- To assess a change in expected pain level from baseline, immediately after the procedure, and again ten minutes after arrival to the recovery room as determined by a 100mm visual analog scale (VAS) for patients with in-room social support during the procedure as compared to those who do not.
- To assess pre- and post-procedure state anxiety levels as determined by the 20-question State-Trait Anxiety Inventory (STAI) for patients with in-room social support as compared to patients without in-room social support.

Secondary Aims:

- To measure acceptability and effectiveness of having social support in the procedure room as reported by the surgical assistant and healthcare providers as determined by a post-procedure questionnaire.
- To evaluate if support was effectively given to the patient as reported by the support person as determined by a post-procedure questionnaire.

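### The protocol's sections do not agree on the between-arm pain comparison, the analysis never names the immediate post-procedure VAS, and the score subtracted is expected pain, recorded when patients may already know their arm

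*Protocol*

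**What the plan says.** Four parts of the protocol describe the pain comparison.

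- **Aim (1.1.2).** The first primary aim is "To assess a change in expected pain level from baseline, immediately after the procedure, and again ten minutes after arrival to the recovery room", with in-room support compared to none. It has two follow-up readings.
- **Design (1.3.1).** The trial is meant "to compare pain and anxiety levels before, during, and after in-clinic abortion in patients with and without a support person".
- **Sample size (1.3.2).** The test is powered for a "difference between the change in pain score from baseline, to during the procedure, to after the procedure between the two groups".
- **Analysis (1.3.11).** The within-group sentence reads "The change in pain score, as assessed by VAS, from baseline to recovery room will be compared within each group". The between-arm sentence opens "Similarly, the difference in the change in VAS scores between the" and goes on to the two study arms and the choice of t or Mann-Whitney test. It names no interval.

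Section 1.3.8.1 and the form in 4.4 define three VAS readings. The first, before the procedure, asks how much pain the patient expects. The second, straight after the procedure, and the third, in recovery, ask about pain at that moment. No item rates pain during the procedure.

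On timing, 1.3.1 states that "Randomization will occur at the beginning of each procedure day by a research assistant", before that day's patients are enrolled. Of allocation within the health center it says "there is no way to avoid patients knowing which arm of the study they are in". Section 1.3.12 concedes that control patients may be more anxious and dissatisfied at baseline because of what they know.

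**The concern.** Two things are at stake.

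First, the support person acts in the procedure room, so the immediate VAS is the reading most likely to show an effect. A reader of 1.3.11 cannot tell whether it is compared between arms. The only interval printed there ends in the recovery room, at least ten minutes after arrival. The aim and the sample-size section each describe something wider.

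Second, a change score compares arms fairly only if allocation cannot have affected the baseline. Here the baseline is an expectation, a different quantity from the pain felt later. It is recorded after the day's arm is drawn, in a trial that does not claim to hide the arm. If control patients expect more pain because they will be alone, their scores appear to fall further. The contrast then moves against the support person with no difference in pain felt.

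**Working it through.** **1. The plan's own figure.** Section 1.3.2 gives 14 per arm for 20 mm, SD 23 mm, 90% power, two-sided 0.05. The two-sample formula gives n per arm = 2 × [23 × (1.960 + 1.282) / 20]² = 27.8, that is 28 per arm, or 29 by the exact t. At 14 per arm the power is about 60%. The value 14 comes from the one-sample formula (13.9), or from a change SD near 16 mm, which is not stated. This is a separate defect. The calculations below use the planned enrolment, read as 100 patients per arm.

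**2. The passages side by side.**

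| Section | Pain readings covered |
|---|---|
| 1.1.2 | expected, immediately after, recovery |
| 1.3.1 | before, during, after |
| 1.3.2 | baseline, during, after; between arms |
| 1.3.11, within arm | baseline to recovery |
| 1.3.11, between arms | no interval named |
| 4.4 (form) | expected; now, at end of procedure; now, in recovery |

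The immediate reading is collected and is part of the aim, but 1.3.11 never names it.

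**3. What subtraction does to precision.** Inputs: "the common standard deviation for VAS scores is 23 mm", which is an SD of scores, not of changes; n = 100 per arm; two-sided 0.05. Assumed: equal SDs, a correlation r between expected and later pain, and no clustering by day. Change SD = 23 × √(2(1 − r)). Power is from the noncentral t.

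| True effect | Change, r = 0 | r = 0.3 | r = 0.5 | r = 0.7 | Direct comparison |
|---|---|---|---|---|---|
| Change SD (mm) | 32.5 | 27.2 | 23.0 | 17.8 | 23 |
| 20 mm | 99% | >99% | >99% | >99% | >99% |
| 10 mm | 58% | 73% | 86% | 98% | 86% |
| 5 mm | 19% | 25% | 33% | 51% | 33% |

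Subtraction costs power below r = 0.5 and gains it above.

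**4. What a shifted expectation does.** Let knowing the arm raise control-day expected pain by d, and let a share k of d carry over to later pain. Then:

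- change-score contrast = effect − d(1 − k)
- direct contrast = effect + kd

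With d = 5 mm and k = 0 (d and k both assumed), the change-score test has this power:

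| True effect | Contrast left | r = 0 | r = 0.3 | r = 0.5 | r = 0.7 |
|---|---|---|---|---|---|
| 20 mm | 15 mm | 90% | 97% | 99.6% | >99.9% |
| 10 mm | 5 mm | 19% | 25% | 33% | 51% |

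Direct comparison at 10 mm keeps 86%. With no true effect, the same 5 mm shift alone gives a significant change-score difference in 19% to 51% of trials. At k = 0.5 the change-score loss is 2.5 mm, and at k = 1 it is zero.

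**5. Covariate adjustment.** Adjusting later pain for a shifted expectation also loses about r × d when k = 0. With effect 10 mm and d = 5 mm, r = 0.1, 0.3 and 0.5 leave about 9.5, 8.5 and 7.5 mm. Expected pain is therefore a safe covariate only if recorded before the patient can know the arm.

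**The case against.** The interval sits in the within-group sentence. The linking word that opens the between-arm sentence may refer only to the choice between parametric and rank tests, and 1.1.2 and 1.3.2 both point to more than one follow-up reading. A reader might infer that the immediate VAS has no between-arm test. The text does not establish that. It leaves the comparison unnamed. This part of the objection stands.

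A reader might also infer that patients do know their arm when they mark expected pain, and that expected pain is shifted. Neither is stated. The remark on knowing the arm in 1.3.1 is given as a reason for not randomising individual patients. Section 1.3.12 speaks of anxiety and dissatisfaction, and its wording leaves room for uncertainty at baseline. The demographic questionnaires in section 4 are headed by arm, but whether patients see that heading is not shown. The shift is a plausible inference and its size is unknown. This part stands too.

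A third objection is that at the planned 20 mm effect the assumed 5 mm shift does little harm to power. That is correct. It does not remove the bias in the estimate, which is d whatever the power.

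Finally, change from expected pain is the stated aim, and dropping it would change the endpoint. That is a fair reason to keep it as a supporting analysis.

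The objection that the analysis plan could settle all this is weaker. The protocol has itself printed an interval, and that interval does not match its own aim.

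**Conclusion.** The point holds as an inconsistency together with a possible bias. Sections 1.1.2, 1.3.2 and 1.3.11 do not agree on the between-arm pain comparison, and the reading closest to the intervention is not named in the analysis. Subtracting expected pain exposes the contrast to a bias of d mm if knowing the arm shifts expectation and not later pain. A higher expectation on control days would work against the support person.

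The size depends on assumptions: d = 5 mm with no carry-over, r from 0 to 0.7, 100 patients per arm, SD 23 mm, and day clustering ignored. Under them, power is 90% or more at 20 mm and 19% to 51% at 10 mm. The documents do not support a claim that the planned pain comparison is underpowered at its own design effect, or that the bias is present. This is a cheap improvement.

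**What to change.** 1. In 1.3.11, name the between-arm comparison at both the immediate post-procedure and the recovery-room VAS. State how the error rate is controlled across the two, by a fixed order or a split alpha. Two unadjusted tests at 0.05 would give up to 1 − 0.95² = 9.75% if independent. With a fixed order that puts the immediate VAS first, the recovery test is not formal if the first fails.
2. Make direct comparison of the reported VAS scores the main pain analysis. Keep change from expected pain as a supporting analysis, so that the stated aim is still reported.
3. Show expected pain by arm. Use it as a covariate only if it is recorded before the patient can know the arm.
4. Align 1.1.2 and 1.3.2 with this. In 1.3.1 and 1.3.2, change the reference to pain during the procedure to pain immediately after it, as on the form.

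Cost: wording in four sections, with a change in which pain analysis leads. No patients, visits or measurements are added, since all three readings are already collected. Precision is lost if r exceeds 0.5 and expectations do not differ by arm (86% against 98% power at 10 mm, r = 0.7). Direct comparison also counts any effect of knowing the arm on later pain as part of the effect (kd).
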